3.4 Data Monitoring Committee

An independent Data Monitoring Committee (DMC) will monitor ongoing safety data at pre-specified time points throughout the study. The DMC will also be responsible for reviewing safety/efficacy results at the time of the interim analysis. The main purpose of the DMC will be to protect the interests of the subjects included in the trial.

The DMC charter will define roles and responsibilities of the study team, DMC members and unblinded team, timing of DMC data reviews as well as the type of data required for each data review meeting.

Upon completion of each data review meeting, the DMC will convey to the sponsor their recommendations as to whether the trial may continue as planned or if the trial should be modified or stopped as specified in the DMC charter. The final decision on whether the study should be modified or stopped will be the responsibility of INmune Bio Inc., the 'sponsor'. Any decision to modify or stop the study will be communicated to investigators and regulatory agencies as well as the full study team by the sponsor.

3.5 Timing of Analyses

An interim analysis will be performed once approximately 20% of participants in the mITT population have completed the Study Day 28 assessment or who have an intercurrent event within 28 days on study. Details are included in Section 6.2.4.

The final analysis will occur once all participants complete their end of study visit or their last scheduled assessment per the Schedule of Assessments (Section 8 of the protocol), or the sponsor terminates the study for futility at time of the interim analysis or for any other reason.

4 ANALYSIS POPULATIONS

Intent-to-treat (ITT) Population: All participants who have signed informed consent, meet inclusion/exclusion criteria, are enrolled in the study and who are randomized to a treatment arm will be included in the ITT population. The ITT will be the analysis population for disposition and demographic reporting purposes. Analyses will be based on the randomized treatment.

Modified Intent-to-treat (mITT) Population: The modified ITT population is a subset of the ITT population and includes participants who have received any amount of INB03 or Placebo. The mITT will be the primary analysis population for all efficacy reporting purposes. Analyses will be based on the randomized treatment.

Per-protocol (PP) Population: All participants included in the mITT population with no major protocol deviation will comprise the PP population. The PP population will be a secondary analysis population for select efficacy endpoints. Analyses will be based on treatment received. Protocol deviations and assignment to the PP population will be done prior to unblinding.

Safety Population (SAF): All participants who have received any amount of INB03 or Placebo are included in the safety set. The SAF will be the analysis population for safety reporting and will be based on treatment received (INB03 or Placebo).

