Sample Size:	
Sample size was calculated on the assumption that participants who meet the enrollment criteria progress to respiratory failure or death 21% of the time given current SOC. Therapy with INB03 is expected to decrease disease progression by two-thirds to 7%. Assuming 90% power and a one-sided alpha level of 0.005, N=346 (173 per arm) are required to observe the expected treatment effect. Assuming approximately 5% of participants are randomized but do not receive treatment, a total of 366 will be randomized to ensure 346 participants receive study drug.
 
Additionally, an interim analysis for futility will be performed when approximately 20% of participants required to observe the expected treatment effect complete the Study Day 28 visit (N~70). Participants evaluated in the interim analysis include those who are randomized and receive study drug and have the Day 28 assessment or who had an intercurrent event prior to Day 28 with early termination (ie: withdrawal of consent, lost to follow-up).
 
A preliminary analysis of the primary efficacy data will be performed prior to final database lock.

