Statistical Methods	
General Methodology:
 
All enrolled participants who are randomized to a study treatment arm will be included in the Intent-to-Treat (ITT) population. The modified ITT (mITT) population is defined as participants who are included in the ITT population who also receive any amount of study drug. The mITT population is the primary analysis population for efficacy analyses.
 
In general, continuous variables will be summarized using number of participants (n), mean, standard deviation (SD), median, minimum, and maximum. Categorical variables will be tabulated with frequency counts and percentages. Where appropriate, 95% confidence intervals (CIs) will be provided. All data will be listed.
 
Efficacy Analysis:
 
The population of interest for all primary and secondary efficacy estimands include participants who are randomized, who have been diagnosed with COVID-19, have at least one co-morbidity, are admitted to the hospital, have pulmonary complications due to COVID-19 and who have received any amount of study drug. This population is considered the mITT population. All primary and secondary efficacy estimands will be evaluated at time of randomization to Study Day 28.
 
Pairwise comparisons between study treatments INB03 + SOC and Placebo + SOC will be performed for each primary and secondary endpoint. The analysis model for the primary endpoint of proportion of participants with disease progression will use a stratified Cochran-Mantel-Haenszel (CMH) test stratified by age (<50, 50-65, >65) and number of co-morbidities (1, 2, 3+) to compare the failure rates of

CONFIDENTIAL

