9.3.1 Intent-to-treat (ITT)

All participants who have signed informed consent, meet inclusion/exclusion criteria, are enrolled in the study and who are randomized to a treatment arm will be included in the ITT population. The ITT will be the analysis population for disposition and demographic reporting purposes. Analyses will be based on the randomized treatment.

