1.1 Changes to the Planned Analysis

The protocol mentions a supplemental analysis will be performed on the ITT population. This analysis will not be performed on this population as the objective of the study is to assess the effect study treatment has on disease progression and patients in the ITT population include those that were randomized but not dosed.

The following sensitivity analyses to assess different strategies for handling intercurrent events have been removed from the analysis as the tipping point analysis will be sufficient in determining robustness of imputation methodologies applied.

- Participants who withdraw consent and have missing disease progression data: The “Composite” strategy will be used. Participants will be considered as having disease progression.
- Participants who withdraw consent and have missing disease progression data: Participants randomized to Placebo will use the “While on Treatment” strategy for this event as described for the primary estimand and participants randomized to INB03 will use the “Composite” strategy.

On 15Jun2021, the sponsor terminated enrollment into the study. A preliminary analysis of the primary efficacy data will be performed prior to full database lock. The SAP was written based on the protocol dated 17May2021 therefore some sections of the SAP may no longer be applicable. Changes from the SAP and protocol defined analyses will be described and justified in the final clinical study report.

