6.1.2 Protocol Deviations

Protocol deviations will be identified and classified as minor or major (violations) before the database is locked. Major protocol deviations include and are not limited to:

- Violation of Inclusion/Exclusion Criteria
- Signed incorrect version of patient consent form
- Use of prohibited therapies
- Receiving incorrect randomized treatment
- Did not receive mechanical ventilation due to the machine not being available

Each protocol deviation will be reviewed prior to database lock and the deviations that are identified as having an impact on the primary study endpoint will be flagged and patients with those deviations will be excluded from the PP population.

Protocol deviations will be summarized by treatment arm and overall for the study.

A listing of protocol deviations will be provided.

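### The documents conflict on whether dosed participants later found ineligible belong in the primary mITT analysis, and the SAP drops the ITT analysis that would have served as a check

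*SAP*

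**What the plan says.** **ITT with an eligibility condition.** SAP 4 restricts ITT to participants who "meet inclusion/exclusion criteria, are enrolled in the study and who are randomized to a treatment arm". Protocol 9.3.1 has the same condition: "All participants who have signed informed consent, meet inclusion/exclusion criteria, are enrolled in the study".

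**mITT inherits it.** Protocol 9.3.2 and SAP 4 define mITT as the part of ITT that received any study drug, and make it the primary efficacy population.

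**ITT without the condition.** The protocol synopsis (Statistical Methods) says: "All enrolled participants who are randomized to a study treatment arm will be included in the Intent-to-Treat (ITT) population". It builds mITT from that by adding only receipt of study drug.

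**Eligibility violations handled elsewhere.** SAP 6.1.2 lists "Violation of Inclusion/Exclusion Criteria" among the major deviations. Deviations judged to affect the primary endpoint lead to exclusion from the PP population, which SAP 4 draws from mITT.

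**A third statement.** SAP 6.2.4 says that those enrolled and randomised by 15 June 2021 go into the primary efficacy analysis. It gives 79 randomised and 77 dosed.

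**The ITT analysis.** Protocol 9.5.1.3 planned a supplementary analysis of the primary endpoint in ITT, with being randomised but undosed handled by treatment policy. SAP 1.1 withdraws it: "This analysis will not be performed on this population". The reason given is that ITT includes undosed patients.

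**The concern.** Two programmers working from these texts could build different primary datasets. One would remove dosed participants found ineligible after randomisation; the other would keep them. Removal after randomisation is a risk because a violation may come to light through closer scrutiny of participants who did badly, and the exclusion is then related to outcome.

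SAP 4 requires assignment before unblinding in its PP definition only. Nothing says that eligibility for ITT or mITT must be judged blind or from pre-randomisation data. SAP 6.2.4 also releases unblinded primary results to selected sponsor staff before final database lock.

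The check that could expose such an effect has gone. The only other population committed for the primary endpoint is PP (SAP 6.2.1.5), which is narrower than mITT. The tipping-point analysis (SAP 6.2.1.4) stays within mITT and varies the handling of missing data, so it cannot bring back excluded participants. With about 77 participants and a one-sided alpha of 0.005, very few people can change the reading of the result.

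**Working it through.** **1. The definitions side by side**

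| Source | Dosed but ineligible: in mITT? | Randomised but undosed: in the primary analysis? |
|---|---|---|
| Protocol 9.3.1 and 9.3.2; SAP 4 (literal) | No | No |
| Protocol synopsis | Yes | No |
| SAP 6.1.2 with the PP definition in SAP 4 | Implied yes | Not addressed |
| SAP 6.2.4 (randomised by 15 June) | Yes | Yes, read literally |

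If ineligible participants were already outside mITT, removing them again from PP would be largely redundant. SAP 6.2.4 differs from SAP 4 on the undosed as well.

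**2. Analyses of the primary endpoint that remain**

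- mITT: primary CMH, tipping point and logistic regression.
- PP: repeat of the primary analysis.
- All randomised: none committed. SAP 6.2 says only that sensitivity and supplemental analyses may be repeated in other populations.

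**3. The plan's own figure**

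The synopsis states: "Assuming 90% power and a one-sided alpha level of 0.005, N=346 (173 per arm) are required to observe the expected treatment effect". The control rate is that participants "progress to respiratory failure or death 21% of the time given current SOC", against 7% on INB03. The unpooled two-proportion formula gives

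n per arm = (2.576 + 1.282)² × (0.21×0.79 + 0.07×0.93) / 0.14² = 14.88 × 0.2310 / 0.0196 = 175.4, so 176 per arm and 352 in total.

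This is within 3% of 346. Power at 173 per arm is 89.5% (unpooled) or 88.5% (pooled). The sample size is not at issue.

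**4. Number outside mITT**

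79 − 77 = 2, and 2/79 = 2.5%. This takes the two not counted as receiving study drug to be undosed. Any dosed participant found ineligible adds to this under the literal reading; that number is not given.

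**5. What a few exclusions could do**

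Assumptions, none of them in the documents: 39 placebo and 38 INB03 participants dosed, event counts as shown, and an unstratified pooled Z. The planned test is a stratified CMH.

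Z = (p_INB03 − p_placebo) / √[p̄(1−p̄)(1/n₁ + 1/n₀)], with one-sided p = Φ(Z).

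Worked once for 3/38 versus 8/39: p̄ = 11/77 = 0.1429; standard error 0.0798; difference −0.1262; Z = −1.58; p = 0.057.

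| Case | INB03 | Placebo | One-sided p |
|---|---|---|---|
| Near the design rates, all 77 dosed | 3/38 | 8/39 | 0.057 |
| One placebo progressor removed | 3/38 | 7/38 | 0.087 |
| Two placebo progressors removed | 3/38 | 6/37 | 0.134 |
| Two INB03 progressors removed | 1/36 | 8/39 | 0.009 |
| Two undosed added to INB03, both progress | 5/40 | 8/39 | 0.168 |
| Two undosed added to INB03, neither progresses | 3/40 | 8/39 | 0.047 |
| Two undosed added to placebo, both progress | 3/38 | 10/41 | 0.024 |
| More extreme case, all 77 dosed | 1/38 | 9/39 | 0.0038 |
| Same, one placebo progressor removed | 1/38 | 8/38 | 0.0065 |

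Near the design rates, no case in the table reaches 0.005. In the more extreme case, one exclusion crosses it.

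**The case against.** A reader might infer that the plan does remove dosed participants after the fact. The documents do not show that. SAP 3.2 says that participants who meet the criteria are the ones to be randomised, so the clause can be read as describing who gets randomised rather than a later filter. No section describes an eligibility review after randomisation for ITT or mITT, and three places point to retention. This stands: what is shown is a conflict, not a removal.

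A reader might also infer that nothing is reported on all randomised participants. That is too broad. Disposition uses the number randomised (SAP 6.1.1), and the Safety Population needs only dosing. The gap concerns efficacy.

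The list in SAP 6.1.2 also feeds the general deviation summary, so its mention of eligibility does not prove that such participants are in mITT. Deviations are to be classified before database lock, which gives some protection, but no rule ties that step to ITT or mITT membership.

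Dropping the ITT analysis is disclosed and reasoned. It was only supplementary, mITT was always primary, and a dosed-only set is defensible in a double-blind trial with two undosed participants. That is fair as far as it goes. The stated reason, however, is the very feature for which the protocol planned the analysis.

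Finally, the threshold crossing rests on hand-picked counts (23% versus 2.6%, more extreme than the planned 21% versus 7%). Fisher's exact test on the same counts gives 0.0079 and 0.0142, both above 0.005. Sensitivity to single events is a feature of any trial this small. The figures show what the ambiguity could matter, not what it did.

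**Conclusion.** The point holds as a conflict over who is in the primary analysis, together with the loss of the only planned all-randomised efficacy analysis of the primary endpoint. Following the stated definition literally would exclude dosed participants after randomisation, with no blinding rule for that decision. The texts pointing to retention make this avoidable but do not settle it.

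The size is uncertain. At least 2 of 79 are outside mITT, and the number of dosed but ineligible participants is unknown and may be zero. Under the assumed split and counts near the design rates, two exclusions move one-sided p from 0.057 to anywhere between about 0.009 and 0.134. Crossing 0.005 through one exclusion needs more extreme counts and depends on the test used. It should be corrected; it does not by itself invalidate the primary analysis.

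**What to change.** 1. In SAP 4, define ITT as all randomised participants by assigned arm, and mITT as ITT participants who received any study drug, regardless of eligibility violations. Make the same change in protocol 9.3.1 if the protocol is amended; otherwise record the departure in SAP 1.1.
2. State that eligibility violations can lead to exclusion from PP only.
3. Align the statement in SAP 6.2.4 on who enters the primary efficacy analysis with mITT (77 dosed).
4. Restore the supplementary ITT analysis of protocol 9.5.1.3 for the primary endpoint on all 79 randomised. Restoring it without step 1 would not be enough, because ITT as now written carries the eligibility condition.

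The cost is a SAP amendment, which SAP section 1 allows if it is approved before final database lock and unblinding, and one repeat of the primary table. The outcomes of the two undosed participants would be used where available. Changing the protocol text as well would need sponsor and ethics committee approval under protocol 10.2; the SAP-only route avoids that.

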5 GENERAL CONSIDERATIONS

5.1 General Data Handling

All analyses will be conducted using SAS 9.4 or higher. Study data will be recorded in electronic case report forms (eCRFs) designed in the VIEDOC v4.63 electronic data capture (EDC) system. Adverse events will be coded using the version 23.1 of the Medical Dictionary for Regulatory Affairs (MedDRA) and prior and concomitant medications will be coded using World Health Organization Drug Dictionary (WHODD) September 2020 version.

Protocol deviation data will be provided in spreadsheet format from the clinical trial management system (CTMS). There are no further vendors for this study.

In general, analysis tables will be presented by treatment arm using the following groupings of subjects:

- INB03
- Placebo
- Overall (background characteristics and safety data only)

Data will be presented in by-patient data listings. Unless otherwise stated, all listings will be sorted by treatment arm, center ID, subject number, and assessment date (and time, if available).

Continuous data will be summarized by treatment group based on number of participants (n), mean, standard deviation (SD), median, minimum value, and maximum value. In some cases, first quartile (Q1) and third quartile (Q3) may also be included.

Categorical data will be summarized by treatment arm using frequency counts and percentages. Where applicable, 95% confidence intervals (CIs) will be provided. Unless otherwise stated, the denominator of percentages will be the number of participants in the population/treatment arm or the number with non-missing data.

- The number of missing values will be presented as a separate category with no percentage, but only if one or more subjects are missing data.
- Counts of zero will be presented without percentages.

Relative to the number of digits after the decimal in the raw data, summary statistics will have the following number of digits after the decimal:

- Minimum and Maximum: same number of significant digits as the raw data
- Mean, Median, Q1, and Q3: one additional significant digit
- SD or Standard Error (SE): two additional significant digits
- Percentages <100% will be reported to one decimal place and percentages of 100% will be reported with no decimal place.
- P-values will be reported to four decimal places. If the value is below 0.0001 it will be noted as < 0.0001; if the value is above 0.9999 it will be noted as > 0.9999.
- Summary statistics will not exceed four digits after the decimal. Some laboratory parameters or other data may require judicious deviation from this rule.

Unless otherwise noted, statistical inference will be based on a 2-sided 1% significance level.

All data up to the time of study completion/withdrawal from the study will be included in the analysis, regardless of duration of treatment.

Numbering for data displays will be based on ICH E3.

5.2 General Definitions

Variable	Definition
Study Day	
• Study Day = date of interest – reference date + 1, when the date of interest \geq reference date;• otherwise, Study Day = date of interest – reference date. 
Note: if either day is missing, reference date calculations will not be performed. Should imputation be performed, then Study day may be derived.

Baseline	Defined as the last non-missing value collected prior to receiving the first dose of study treatment (based on date and time of administration as applicable).
Post-baseline	Defined as values collected after receipt of the first dose of study treatment (based on date and time of administration as applicable)
Change from Baseline	Defined as: Post-baseline value – Baseline value

Percent Change from Baseline	Defined as: (Post-baseline value – Baseline value)/Baseline value x 100. Note: To compute percent change from baseline, the baseline value cannot be equal to zero.
Duration on Study	End of study date – randomization date +1.
Disease Onset	Self-reported start date of first COVID-19 symptom – date of first dose of study treatment. Time will be considered in the derivation if collected for both dates. If the self-reported date is missing, the date of positive COVID-19 test will be used.
Duration of Adverse Event (in days)	
 • Stop date of event – start date of event + 1, if time is not collected. • (Stop date/time of event – start date/time of event)/24, if time is collected.
Months	Divide by 30.4375
Year	Divide by 365.25
Week	Divide by 7

5.3 Data Imputation Rules

Generally, missing data will not be imputed, and will be presented as collected in the study database.

In cases where AE or medication dates are missing, the imputation methods described in Appendix 1 will be used to determine flags for treatment-emergent events and concomitant medications.

For interim reporting purposes or ongoing reporting needs, treatment or study end dates will be imputed as the earliest of the data cutoff date, date of death, or date of treatment study withdrawal.

Other missing data methods specific to statistical analysis will be proposed within the respective analysis section, as needed.

5.4 Visit Windows

In general, data will be summarized and listed using the recorded nominal visit values in the eCRF, regardless of the actual study day on which a value was collected. Unscheduled visits will not be summarized in tables but will be presented in data listings.

